6.9.1. Rescue Treatment

Descriptive statistics for drug accountability of topical low and moderate potency rescue medication provided by the sponsor will also be supplied, including the amount utilized throughout treatment (from Week 0 through Week 16 in the primary outcome lock). The total amount in grams for low and moderate potency will be summarized between scheduled visits (Week 0 through Week 1, Week 1 through Week 2, Week 2 through Week 4, Week 4 through Week 8, Week 8 through 12, Week 12 through Week 16), as well as throughout the treatment period from Week 0 through Week 16.

The total amount will also be presented for the all visit intervals, irrespective of potency. If a returned tube is not weighed in grams, then the tube can be classified as partially used, fully used, unused, or unknown. Partially used rescue medication tubes will be considered to be 50% used, whereas Fully Used and Unused will be considered as 100% used and 0% used, respectively. When drug accountability is not performed for a particular tube of rescue medication or an answer of Unknown is given for a tube which is not returned, that particular tube will not be included in the analysis.

The number of days rescue therapy is used for each patient is also collected on the diary device. The proportion of time that the patients did not use rescue therapy will be summarized for the aforementioned visit intervals by potency (low or moderate) and both potencies combined. For this analysis, the date of the first entry on the diary device will be used to signify the first day of rescue therapy use.

Additionally, a summary of the initial rescue therapy and the reason for rescue will be produced, as well as a summary of the proportion of patients rescued at each study visit up to week 16. A summary of all rescue medications will be provided.

6.10. Previous and Concomitant Therapy

Summaries of previous and concomitant medications will be based on the ITT population.

At screening, previous and current AD treatments are recorded for each patient. A summary of previous medications used for AD, as well as zoster and TB vaccine, and medications that are discontinued after screening and before the first dose of study drug, will be prepared using frequency counts and percentages by preferred medication name, with preferred medication

names sorted by frequency in the baricitinib 2-mg group. Concomitant therapy will be recorded at each visit and will be classified similarly.

Concomitant therapy for the treatment period is defined as therapy that starts before or during the treatment periods and ends during the treatment period or is ongoing (has no end date or ends after the treatment period). Should there be insufficient data to make this comparison (eg, the concomitant therapy stop year is the same as the treatment start year, but the concomitant therapy stop month and day are missing), the medication will be considered as concomitant for the treatment period.

Summaries of previous medications will be provided for the following category: previous AD therapies

Summaries of concomitant medications will be provided for the following category: concomitant medications excluding rescue medicine

6.11. Efficacy Analyses

The general methods used to summarize efficacy data, including the definition of baseline value for assessments, are described in Section 6.2. Efficacy analyses will generally be analyzed according to the following formats and patients will be analyzed according to the investigational product to which they were randomized at Week 0 (Visit 2):

- Week 0 to Week 16, with primary censoring rule
- Week 0 to Week 16, with secondary censoring rule for primary and key secondary objectives.
- Week 16 to Week 104, using descriptive statistics for objectives as specified in the other secondary and exploratory objectives, (Note: will not be completed for the Week-16 primary outcome DBL, but will be completed for subsequent DBLs)

Table JAIW.6.4 includes the descriptions and derivations of the primary, secondary, and exploratory efficacy outcomes.

Table JAIW.6.5 provides the detailed analyses including analysis type, method and imputation, population, time point, and comparisons for efficacy analyses.

Table JAIW.6.4. Description and Derivation of Primary, Secondary, and Exploratory Efficacy Outcomes

Measure	Description	Variable	Derivation/Comment	Imputation Approach if Missing Components
Eczema Area and Severity Index (EASI)	
The EASI assesses objective physician estimates of 2 dimensions of AD, disease extent and clinical signs (Hanifin et al. 2001), by scoring the extent of disease (percentage of skin affected: 0 = 0%; 1 = 1-9%; 2 = 10-29%; 3 = 30-49%; 4 = 50-69%; 5 = 70-89%; 6 = 90-100%) and the severity of 4 clinical signs (erythema, edema/papulation, excoriation, and lichenification), each on a scale of 0-3 (0 = none, absent; 1 = mild; 2 = moderate; 3 = severe) at 4 body sites (head and neck, trunk, upper limbs, and lower limbs). Half scores are allowed between severities 1, 2 and 3. Each body site will have a score that ranges from 0-72, and the final EASI score will be obtained by weight averaging these 4 scores. Hence, the final EASI score will range from 0-72 for each time point.
	
 ▪ EASI score ▪ EASI50 ▪ EASI75 ▪ EASI90 	
Derive EASI region score for each of head and neck, trunk, upper limbs, and lower limbs as follows:
 $\text{EASI}_{\text{region}} = (\text{Erythema} + \text{edema/papulation} + \text{Excoriation} + \text{Lichenification}) * (\text{value from percentage involvement})$ 
where erythema, edema/papulation, excoriation, and lichenification are evaluated on a scale of 0-3 and value from percentage involvement is on a scale of 0-6.
 
Then total EASI score is as follows:
 $\text{EASI} = 0.1 * \text{EASI}_{\text{head and neck}} + 0.3 * \text{EASI}_{\text{trunk}} + 0.2 * \text{EASI}_{\text{upper limbs}} + 0.4 * \text{EASI}_{\text{lower limbs}}$	
N/A – partial assessments cannot be saved.

Measure	Description	Variable	Derivation/Comment	Imputation Approach if Missing Components
		
 ▪ Change from baseline in EASI score ▪ Percent change from baseline EASI score 	
Change from baseline: observed EASI score – baseline EASI score
 
% change from baseline: $100 \times \frac{\text{Observed score} - \text{Baseline}}{\text{Baseline}}$
	Missing if baseline or observed value is missing
Body Surface Area (BSA) Affected by AD	BSA affected by AD will be assessed for 4 separate body regions and is collected as part of the EASI assessment: head and neck, trunk (including genital region), upper extremities, and lower extremities (including the buttocks). Each body region will be assessed for disease extent ranging from 0% to 100% involvement. The overall total percentage will be reported based off of all 4 body regions combined, after applying specific multipliers to the different body regions to account for the percent of the total BSA represented by each of the 4 regions.	
 ▪ BSA score ▪ Change from baseline in BSA score 	
Use the percentage of skin affected for each region (0 to 100%) in EASI as follows:
 
Change from baseline: observed BSA score – baseline BSA score
	
N/A – partial assessments cannot be saved.
 
Missing if baseline or observed value is missing.

Measure	Description	Variable	Derivation/Comment	Imputation Approach if Missing Components
Validated Investigator's Global Assessment for AD (IGA)	The validated IGA based on a static, numeric 5-point scale from 0 (clear) to 4 (severe). The score is based on an overall assessment of the degree of erythema, papulation/induration, oozing/crusting, and lichenification.	
 ▪ IGA score ▪ Change from baseline in IGA score ▪ IGA[0,1] with ≥ 2-point improvement ▪ IGA[0] ▪ Time to IGA (0,1) 	
Single item. Range: 0 to 4 0 represents "clear" 4 represents "severe"
 
Change from baseline: observed IGA score – baseline IGA score
 
 ▪ Observed score of 0 or 1 and change from baseline ≤ 2 ▪ Observed score of 0 
▪ first time reaching IGA (0,1) as event 1, rescue and discontinue for lack of efficacy as event 2, censor up to Week 16
	
Single item, missing if missing.
 
Missing if baseline or observed value is missing.
 
 ▪ Missing if baseline or observed value is missing. ▪ Single item, missing if missing. 
▪ Use observed value, rescue and discontinue for lack of efficacy as competing event, censor up to Week 16

SCORing Atopic Dermatitis (SCORAD)		
 ▪ SCORAD score ▪ Change from baseline in SCORAD score ▪ Percent change from baseline in SCORAD score 	
SCORAD = A/5 + 7B/2 + C, where A is extent of disease, range 0-100 B is disease severity, range 0-18 C is subjective symptoms, range 0-20
 
Change from baseline: observed SCORAD score – baseline SCORAD score % change from baseline: $100 \times \frac{\text{Observed score} - \text{Baseline}}{\text{Baseline}}$ 
	
Missing if components A and B are missing or if component C is missing. Partial assessments performed by physician cannot be saved and partial assessments performed by subject cannot be saved.
 
Missing if baseline or observed value is missing

Measure	Description	Variable	Derivation/Comment	Imputation Approach if Missing Components
	
The SCORAD index uses the rule of nines to assess disease extent (head and neck 9%; upper limbs 9% each; lower limbs 18% each; anterior trunk 18%; back 18%; and genitals 1%). It evaluates 6 clinical characteristics to determine disease severity: (1) erythema, (2) edema/papulation, (3) oozing/crusts, (4) excoriation, (5) lichenification, and (6) dryness on a scale of 0 to 3 (0=absence, 1=mild, 2=moderate, 3=severe). The SCORAD index also assesses subjective symptoms of pruritus and sleep loss in the last 72 hours on visual analogue scales (VAS) of 0 to 10 where 0 is no itch or sleep loss and 10 is worst imaginable itch or sleep loss. These 3 aspects: extent of disease, disease severity, and subjective symptoms combine to give a maximum possible score of 103 (ETFAD 1993; Kunz et al. 1997; Schram et al. 2012).
	
 ▪ SCORAD75 ▪ SCORAD90 	
% Improvement in SCORAD from baseline $\geq 75\%$: % change from baseline ≤ -75
 
% Improvement in SCORAD from baseline $\geq 90\%$: % change from baseline ≤ -90
	
Missing if baseline or observed value is missing
 
Missing if baseline or observed value is missing

Abbreviations: AD = atopic dermatitis; N/A = not applicable.

Table JAIW.6.5. Description of Primary, Secondary and Exploratory Efficacy Analyses

Measure	Variable	Analysis Method (Section 6.2.4)	Population (Section 6.2.2)	Comparison ^a /Time Point	Analysis Type
Eczema Area and Severity Index (EASI) [categorical]	Proportion of patients achieving EASI75	Logistic regression using NRI (both censoring rules, respectively)	ITT	Bari 2 mg or Bari 1 mg vs PBO; Week 16	Primary analysis(Bari 2-mg vs PBO) Key secondary analysis (Bari 1-mg vs PBO) /secondary censoring rule, sensitivity analysis
		Logistic regression using NRI (primary censoring rule)	PPS	Bari 2 mg vs PBO; Week 16	Sensitivity analysis
		Logistic regression using pMI (primary censoring rule)	ITT	Bari 2 mg or Bari 1 mg vs PBO; Week 16	Sensitivity analysis
		Logistic regression using Tipping Point (primary censoring rule)	ITT	Bari 2 mg or Bari 1 mg vs PBO; Week 16	Sensitivity analysis
		Cumulative Incidence Function of Time to reaching EASI 75% reduction (primary censoring rule)	ITT	Bari 2 mg or Bari 1 mg vs PBO; Week 16	Exploratory analysis
	Proportion of patients achieving EASI90	Descriptive using observed and mLOCF	Week 16 Responders	PBO, Bari 1 mg, Bari 2 mg; Week 16-104	Exploratory analysis in Final DBL
		Logistic regression using NRI (both censoring rules, respectively)	ITT	Bari 2 mg or Bari 1 mg vs PBO; Week 16	Key secondary analysis/secondary censoring rule, sensitivity analysis
		Logistic regression using pMI (primary censoring rule)	ITT	Bari 2 mg or Bari 1 mg vs PBO; Week 16	Sensitivity analysis
	Proportion of patients achieving EASI50	Logistic regression using NRI (primary censoring rule)	ITT	Bari 2 mg or Bari 1 mg vs PBO; Week 16	Secondary analysis
Eczema Area and Severity Index (EASI) [continuous]	EASI score % change from baseline	MMRM (both censoring rules, respectively)	ITT	Bari 2 mg or Bari 1 mg vs PBO; Week 16	Key secondary analysis/secondary censoring rule, sensitivity analysis

Measure	Variable	Analysis Method (Section 6.2.4)	Population (Section 6.2.2)	Comparison ^a /Time Point	Analysis Type
		ANCOVA; pMI (primary censoring rule)	ITT	Bari 2 mg or Bari 1 mg vs PBO; Week 16	Sensitivity analysis
		ANCOVA; mLOCF (primary censoring rule)	ITT	Bari 2 mg or Bari 1 mg vs PBO; Week 16	Sensitivity analysis
		ANCOVA; mBOCF (primary censoring rule)	ITT	Bari 2 mg or Bari 1 mg vs PBO; Week 16	Sensitivity analysis
		Descriptive using observed and mLOCF	Week 16 Responders	PBO, Bari 1 mg, Bari 2 mg; Week 16-104	Exploratory analysis in Final DBL
	EASI score change from baseline	MMRM (primary censoring rule)	ITT	Bari 2 mg or Bari 1 mg vs PBO; Week 16	Exploratory analysis
		Descriptive using observed and mLOCF	Week 16 Responders	PBO, Bari 1 mg, Bari 2 mg; Week 16-104	Exploratory analysis in Final DBL
Validated Investigator's Global Assessment for AD (IGA)	Proportion of patients achieving IGA [0,1] with a ≥ 2 -point improvement	Logistic regression using NRI (both censoring rules, respectively)	ITT	Bari 2 mg or Bari 1 mg vs PBO; Week 16	Key secondary analysis/secondary censoring rule, sensitivity analysis
		Logistic regression using pMI (primary censoring rule)	ITT	Bari 2 mg or Bari 1 mg vs PBO; Week 16	Sensitivity analysis
		Tipping point analysis (primary censoring rule)	ITT	Bari 2 mg or Bari 1 mg vs PBO; Week 16	Sensitivity analysis
		Cumulative Incidence Function of Time to reaching IGA (0,1) reduction (primary censoring rule)	ITT	Bari 2 mg, 1 mg vs PBO; Weeks 0 to 16	Exploratory analysis
	Proportion of patients achieving IGA [0,1] with a ≥ 2 -point improvement	Logistic regression using NRI (primary censoring rule)	ITT	Bari 2 mg or Bari 1 mg vs PBO; Week 4	Secondary analysis

Measure	Variable	Analysis Method (Section 6.2.4)	Population (Section 6.2.2)	Comparison ^a /Time Point	Analysis Type
	Proportion of patients achieving IGA [0]	Logistic regression using NRI (primary censoring rule)	ITT	Bari 2 mg or Bari 1 mg vs PBO; Week 16	Secondary analysis
	Proportion of patients achieving IGA [0, 1]	Descriptive using observed and mLOCF	Week 16 Responders	PBO, Bari 1 mg, Bari 2 mg; Week 16-104	Exploratory analysis in Final DBL
Body Surface Area (BSA) Affected by AD	BSA change from baseline	MMRM & ANCOVA; mLOCF (primary censoring rule)	ITT	Bari 2 mg or Bari 1 mg vs PBO; Week 16	Secondary analysis/ANCOVA with mLOCF, sensitivity analysis
SCORing AD (SCORAD) [categorical]	Proportion of patients achieving SCORAD75	Logistic regression using NRI (both censoring rules, respectively)	ITT	Bari 2 mg or Bari 1 mg vs PBO; Week 16	Key secondary analysis/secondary censoring rule, sensitivity analysis
		Logistic regression using pMI (primary censoring rule)	ITT	Bari 2 mg or Bari 1 mg vs PBO; Week 16	Sensitivity analysis
		Descriptive using observed and mLOCF	Week 16 Responders	PBO, Bari 1 mg, Bari 2 mg; Week 16-104	Exploratory analysis in Final DBL
	Proportion of patients achieving SCORAD90	Logistic regression using NRI (primary censoring rule)	ITT	Bari 2 mg or Bari 1 mg vs PBO; Week 16	Secondary analysis
SCORing AD (SCORAD) [continuous]	SCORAD score change from baseline	MMRM & ANCOVA; mLOCF (primary censoring rule)	ITT	Bari 2 mg or Bari 1 mg vs PBO; Week 16	Secondary analysis/ANCOVA with mLOCF, sensitivity analysis
		Descriptive using observed and mLOCF	Week 16 Responders	PBO, Bari 1 mg, Bari 2 mg; Week 16-104	Exploratory analysis in Final DBL
	SCORAD score % change from baseline	MMRM (primary censoring rule)	ITT	Bari 2 mg or Bari 1 mg vs PBO; Week 16	Exploratory analysis

Measure	Variable	Analysis Method (Section 6.2.4)	Population (Section 6.2.2)	Comparison ^a /Time Point	Analysis Type
		Descriptive using observed and mLOCF	Week 16 Responders	PBO, Bari 1 mg, Bari 2 mg; Week 16-104	Exploratory analysis in Final DBL
Skin Infections	Proportion of patients developing skin infections requiring antibiotic treatment	Fisher's exact	ITT	Bari 2 mg or Bari 1 mg vs PBO; Week 16	Secondary analysis

Abbreviations: AD = atopic dermatitis; ANCOVA = analysis of covariance; Bari = baricitinib; DBL = database lock; ITT = intent-to-treat; mBOCF= modified baseline observation carried forward; mBOCF = modified baseline observation carried forward; mLOCF = modified last observation carried forward; MMRM = mixed model repeated measures; NRI = nonresponder imputation; PBO = placebo; PPS = per-protocol set; pMI = placebo multiple imputation.

6.11.1. Primary Outcome and Methodology

Both EASI score and IGAs are commonly used in clinical trials, both for qualifying patients for enrollment and for evaluating treatment efficacy (Langley et al. 2015; Futamura et al. 2016; Bożek and Reich 2017). There is no single “gold standard” disease severity scale for AD; however, IGA scales provide clinically meaningful measures to patients and investigators that are easily described and that correspond to disease severity categories (for example, moderate to severe), and a 75% improvement from Baseline (EASI75) is a commonly used measure of treatment effect in AD clinical trials.

The primary analysis of the study is to test the hypothesis that baricitinib 2-mg is superior to placebo when evaluating the proportion of patients achieving EASI75 at Week 16 using the ITT population, assuming the treatment response disappears after patients are rescued or discontinue from study or treatment. This will serve as the primary estimand. In this estimand, missing data due to the application of the primary censoring rule and the occurrence of other non-censor intercurrent events will be imputed using the NRI method described in Section [6.4.1](#).

A supplemental estimand is to test the hypothesis that baricitinib 2-mg is superior to placebo when evaluating the proportion of patients achieving EASI75 at Week 16 using the ITT population, assuming the treatment response disappears after patients discontinue from study or treatment. In this supplemental estimand, missing data due to the application of the secondary censoring rule and the occurrence of other non-censor intercurrent events will be imputed using the NRI method described in Section [6.4.1](#).

A logistic regression analysis will be used for the treatment group comparisons. The odds ratio, corresponding 95% CIs, and p-value, as well as the treatment differences and the corresponding 95% CIs, will be reported. Missing data will be imputed using the NRI method described in Section [6.4.1](#).

Multiplicity-controlled analyses will be performed on the primary and key secondary (see Section [4.2.1](#)) objectives in order to control the overall Type I error rate at a 2-sided alpha level of 0.05. A graphical approach will be used to perform the multiplicity controlled analyses as described in Section [6.6](#).

6.11.2. Secondary and Exploratory Efficacy Analyses

For secondary analysis, the null hypotheses is that neither baricitinib 2-mg nor baricitinib 1-mg is superior to placebo in the ITT population. These analyses assume treatment response disappears after patients are rescued or permanently discontinued from treatment and will serve as the primary estimand. In this estimand, missing data due to the application of the primary censoring rule and the occurrence of other non-censor intercurrent events will be imputed using the method described in [Table JAIW.6.1](#).

There will be no adjustment for multiple comparisons for any other analyses. The secondary and exploratory efficacy analyses are detailed in [Table JAIW.6.5](#). Health outcomes analyses are described in Section [6.12](#).

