6.4. Handling of Dropouts or Missing Data

Intercurrent events (International Conference on Harmonisation [ICH] E9 R1) are events which occur after the treatment initiation and make it impossible to measure a variable or influence how it would be interpreted.

Depending on the estimand being addressed, different methods will be used to handle missing data as a result of intercurrent events. Intercurrent events can occur through the following:

- application of one of the censoring rules (including after permanent study drug discontinuation, after rescue therapy)
- discontinuation from the study

- missing an intermediate visit prior to discontinuation or rescue, and
- lost to follow-up.

Non-censor intercurrent events are events that are not due to the application of any censoring rule (ie, the last 3 items in the list above).

Note that as efficacy and health outcome data can accrue after a patient permanently discontinues study drug or begins rescue therapy, specific general censoring rules to the data will be applied to all efficacy and health outcome observations subsequent to these events depending on the estimand being addressed. These specific censoring rules applied to Week 16 interim analyses are described below.

The *primary censoring rule* will censor efficacy and health outcome data after permanent study drug discontinuation or after rescue therapy. This censoring rule will be applied to all continuous and categorical efficacy and health outcome endpoints. Alternatively, this censoring rule is equivalent to using all the data up to rescue.

A *secondary censoring rule* will only censor efficacy and health outcome data after permanent study drug discontinuation. As patients who are rescued to systemic therapies are required to permanently discontinue study drug, they will also have post-rescue observations censored. The secondary censoring rule will be applied to primary and key secondary efficacy and health outcome endpoints.

After Week 16, concomitant use of low-potency TCS is allowed. Data collected after permanent study drug discontinuation is excluded. This rule will be applied to the final DBL.

Non-responder imputation (for categorical variables) and MMRM (for continuous variables) will be the primary methods used to handle missing data. Censoring rules, along with their associated estimator assumptions, are described in Sections 6.4.1 through 6.4.6.

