Table JAIW.6.1 summarizes how imputation techniques and censoring rules are applied to efficacy and health outcome endpoints.

Table JAIW.6.1. Imputation Techniques for Various Variables

Efficacy and Health Outcome Endpoints	Imputation Method
IGA(0,1), EASI75, 4-point Itch NRS improvement	NRI ^{ab} , pMI ^a , Tipping point ^a , mLOCF
EASI90, SCORAD75	NRI ^{ab} , pMI ^a
EASI percent change, ADSS Item 2 change, Skin Pain NRS change	MMRM ^{ab} , mLOCF ^a , pMI ^a , mBOCF ^a
All remaining categorical measures	NRI ^a , mLOCF
All remaining continuous efficacy and health outcome measures in secondary analysis	MMRM ^a , mLOCF ^a
All continuous efficacy and health outcome measures in exploratory analysis	MMRM ^a

Abbreviations: AD = atopic dermatitis; ADSS = Atopic Dermatitis Sleep Scale; EASI = Eczema Area and Severity Index score; IGA = Investigator's Global Assessment for AD; mBOCF = baseline observation carried forward; mLOCF = modified last observation carried forward; MMRM = mixed model repeated measures; NRI = nonresponder imputation, NRS = Numeric Rating Scale; pMI = placebo multiple imputation; SCORAD = SCORing Atopic Dermatitis.

- a Analyses utilizing the primary censoring rule.
- b Analyses utilizing the secondary censoring rule.

Tipping Point, pMI, NRI, and MMRM (etc.) were used in the Week 16 interim DBL. The Final DBL only use observed and mLOCF.

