6.4.2. Mixed Model for Repeated Measures

Mixed model for repeated measures analyses will be performed on continuous endpoints to mitigate the impact of missing data. This approach assumes missing observations are missing-at-random (missingness is related to observed data) and borrows information from patients in the same treatment arm taking into account both the missingness of data through the correlation of the repeated measurements.

Essentially MMRM estimates the treatment effects had all patients remained on their initial treatment throughout the study. For this reason, the MMRM imputation implies a different estimand (hypothetical strategy [ICH E9 R1]) than the one used for NRI on categorical outcomes.

All continuous endpoints will utilize MMRM after applying the primary censoring rule. As sensitivity analyses, all key secondary continuous endpoints will also utilize MMRM after applying the secondary censoring rule ([Table JAIW.6.1](#)).

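### SAP 6.11.2 gives secondary efficacy analyses a loss-of-response estimand without restriction, but its continuous endpoints are analysed by MMRM, which 6.4.2 says targets a different, hypothetical effect

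*SAP*

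**What the plan says.** Section 6.11.2 states the null hypothesis for the secondary analyses in the ITT population and continues: "These analyses assume treatment response disappears after patients are rescued or permanently discontinued from treatment". The same sentence makes this the primary estimand. It then refers to Table JAIW.6.1 for the handling of data missing after the primary censoring rule or other intercurrent events. Nothing in the paragraph confines it to binary endpoints.

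In Table JAIW.6.1 the row "EASI percent change, ADSS Item 2 change, Skin Pain NRS change" lists MMRM first, followed by mLOCF, pMI and mBOCF. Section 6.4 says: "Non-responder imputation (for categorical variables) and MMRM (for continuous variables) will be the primary methods used to handle missing data". Section 6.4.2 adds: "All continuous endpoints will utilize MMRM after applying the primary censoring rule". Table JAIW.6.5 labels MMRM of EASI percent change the key secondary analysis, and MMRM of BSA change and SCORAD change the secondary analysis.

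On what MMRM estimates, Section 6.4.2 says that it assumes data missing at random, and: "Essentially MMRM estimates the treatment effects had all patients remained on their initial treatment throughout the study". It concludes that "the MMRM imputation implies a different estimand (hypothetical strategy [ICH E9 R1]) than the one used for NRI on categorical outcomes".

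**The concern.** The same endpoints carry two incompatible descriptions of the effect being estimated. Under 6.11.2, a patient who is rescued or stops treatment counts as having lost the response. Under 6.4.2, the estimate describes what would have happened had that patient stayed on the assigned treatment. MMRM on data censored at rescue or discontinuation delivers the second, not the first.

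What is at stake is interpretation. H2,2 (EASI percent change, 2 mg) receives alpha directly after the primary hypothesis, so it is the first secondary result to be read. Anyone who takes its estimand from 6.11.2, the section on secondary efficacy, would read the MMRM difference as already penalising rescue and discontinuation. It does not.

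**Working it through.** **Is there a figure to reproduce?** None bears on this point. The SAP's power statement concerns EASI75. With 150 per arm, 20% versus 10% and two-sided 0.05, a pooled chi-squared calculation gives 68.1%, against the stated 68%. Nothing here depends on it.

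**The sections side by side**

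- 6.11.1, primary endpoint: loss of response after rescue or discontinuation, with NRI. Consistent, because 6.4.1 attaches exactly that assumption to NRI under the composite strategy.
- 6.11.2, secondary endpoints: the same assumption, but the method comes from Table JAIW.6.1. Consistent for categorical endpoints (NRI), inconsistent for continuous ones (MMRM).
- 6.4.2: says outright that MMRM and NRI imply different estimands.
- 6.4.4: mBOCF assumes the effect is lost and the patient returns to baseline. It is planned for the continuous key secondaries, as a sensitivity analysis.
- 6.4.5: pMI assumes that patients behave after the event as if on placebo. It is planned for the key secondaries at Week 16, also as a sensitivity analysis.

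The two methods that assume loss of benefit for continuous endpoints are thus sensitivity analyses, while the main analysis assumes something else.

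**Which endpoints are reached**

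- Directly under 6.11.2 and Table JAIW.6.5: EASI percent change (H2,2 and H1,2), BSA change, SCORAD change.
- By extension: 6.11.2 refers health outcomes to 6.12, which says they generally follow the formats of 6.11. This covers the MMRM-analysed health outcomes, including Skin Pain NRS (H2,4, H1,4) and ADSS Item 2 (H2,9, H2,10, H1,9, H1,10).
- Section 6.6 lists 24 hypotheses, 12 per dose. Eight are continuous: two reached directly and six by extension.

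**Can the gap be sized?** Not from the SAP, which gives neither expected EASI changes nor intercurrent-event rates. As an illustration only, assume on-treatment mean EASI changes of -50% (active) and -30% (placebo), the same on-treatment mean in patients with and without events, and return to baseline after an event. With event proportions f_a (active) and f_p (placebo):

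- Hypothetical difference: -50 - (-30) = -20, whatever the event rates.
- Loss-of-response difference: -50(1 - f_a) + 30(1 - f_p) = -20 + 50 f_a - 30 f_p.

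| f_a / f_p | Loss-of-response difference |
|---|---|
| 10% / 10% | -18 |
| 10% / 20% | -21 |
| 10% / 30% | -24 |
| 20% / 30% | -19 |
| 30% / 30% | -14 |
| 35% / 35% | -13 |

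Against -20, these run from 35% smaller (7/20) to 20% larger (4/20). Under these means the loss-of-response effect is the larger one whenever 30 f_p exceeds 50 f_a, that is, when the placebo event rate is more than 5/3 of the active rate.

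**The case against.** The best reply is that the SAP already states the right estimand where it matters. Section 6.4 says the methods depend on the estimand, 6.4.1 ties loss of effect to NRI, and 6.4.2 names the hypothetical strategy for MMRM. On this view 6.11.2 is a loose summary that carries over the primary-endpoint wording. No estimate, p-value, alpha step or sample size would change. All of this is correct about the analyses, and it limits the point to interpretation. But 6.4.2 shows the 6.11.2 sentence to be wrong without amending it, and 6.11.2 is the section that states the secondary estimand.

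The scope also needs care. A reader might infer that 6.11.2 directly mislabels all eight continuous alpha-controlled hypotheses. It does not. Six belong to 6.12, which adopts the formats of 6.11 only in general terms, and 6.11 describes those formats as time windows with censoring rules or descriptive statistics, not as an estimand.

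A reader might also infer that mBOCF is the one correct estimator under loss of benefit. Section 6.4.5 describes pMI as assuming no pharmacological benefit after the event, so the SAP plans two such analyses with different assumptions. Finally, it cannot be assumed that a report would repeat the 6.11.2 description, since 6.4.2 is equally part of the plan.

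**Conclusion.** The point holds as an error in the stated estimand. It is direct for EASI percent change, BSA change and SCORAD change, and extends through 6.12 to the MMRM-analysed health outcomes. It changes what the continuous secondary results can be said to show, including H2,2.

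Two stronger readings are not supported. One is that the wrong analysis would be run or that type I error control is affected: Sections 6.4, 6.4.2 and Table JAIW.6.5 agree on MMRM with the primary censoring rule. The other is that MMRM overstates the effect relative to loss of response: the illustration goes in both directions, and its inputs (-50%, -30% and event rates of 10% to 35%) are assumptions. At ADSS Week 1 few events are likely, so any numerical gap there may be small. The conclusion rests on the SAP's own wording and not on the illustration.

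**What to change.** - In 6.11.2, limit the loss-of-response (composite) statement to categorical secondaries analysed with NRI.
- In the same paragraph, state that continuous secondaries analysed with MMRM under the primary censoring rule target the hypothetical strategy of 6.4.2.
- Carry the same statement into 6.12.
- For the continuous key secondaries, report mBOCF and pMI beside MMRM as the results under loss of benefit after intercurrent events, labelled return to baseline and placebo-like behaviour respectively. Table JAIW.6.7 plans pMI for ADSS Item 2 at Week 16 only, so at Week 1 mBOCF stands alone.

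The cost is wording and table labels. Both sensitivity analyses are already planned, and no sample size, alpha allocation or main analysis changes. The SAP describes the Week 16 lock as already executed, so the correction bears on how those results are described and calls for no re-analysis.
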